Title: The Role of a Nasal Bridle in the Frequency of Repeat Endoscopic Procedures for Endoscopic Nasoenteric Tube Placement

ClinicalTrials.gov ID: NCT03966157

Documentation upload date: 3/22/2023

Initial IRB approval date: 06/13/2019

Brief Summary:

In critically ill patients, nutrition is a major part of healing and recovery. In patients unable to tolerate oral feeding, nasoenteric tube feeding (a tube placed from the nose to the stomach or small intestine) provides a safe alternative for feeding. Some patients require these tubes to be placed endoscopically due to numerous patient factors including difficult anatomy, need for post-gastric feeding, among others). In patients that require endoscopically placed tubes, there is risk of perforation, infection, bleeding, aspiration, and rarely even death. In patients that have recurrent dislodgement of endoscopically placed tubes, the need for repeat endoscopy increases patient exposure to these risks. Traditional securing mechanism with adhesive tape to reduce dislodgment often fail in critically ill patients requiring patients to have repeat endoscopies to replace nasoenteric feeding tubes and subjects patients potentially to increased cumulative risks associated with each endoscopy.

The investigators propose to collect data for one year, the investigators will prospectively follow via chart review endoscopically placed nasoenteric tubes placed with a Standard AMT Bridle securement device and assess if there is a reduction in accidental tube removal requiring replacement endoscopically.

Outcomes:

Primary objective is to see if nasal bridles versus standard adhesive tape to secure nasoenteric tubes decreases the need for repeat endoscopy to replace dislodged nasoenteric tubes. The number of endoscopies and repeated nasoenteric tubes placed will be tracked at six and twelve months. Secondary objectives can assess if reduces tube dislodgement frequency. Hypothesis: We hypothesize that nasal bridles in endoscopically placed feeding tubes will reduce the number of unnecessary endoscopies reducing health care costs and complications.

Detailed Description:

Patients to be recruited are those who are scheduled to undergo routine upper endoscopy with nasoenteric tube placement. Patients will be randomized into two groups: control arm and device arm.

Control arm includes patients that will have nasoenteric tubes secured with standard protocol, adhesive tape. Device arm includes patients that will have nasoenteric tubes secured with Standard AMT Bridle. The nasal bridles will be placed by the endoscopist. Upper endoscopy will not be affected. Placement of nasal bridle will take 1-2 minutes after endoscopic procedure completed. No addition sedation, medication or exposure necessary.

Patients will be randomized by sealed envelope randomization. Clinicians are given randomly generated treatment allocations within sealed opaque envelopes. Once a patient has consented to enter the study

trial an envelope is opened and the patient is then offered the allocated treatment regimen. Patients will be consented by a member of the research team prior to endoscopy. Randomization will be singly blinded only to the patient prior to endoscopy. Endoscopist will not be blinded as they will be placing the securement device and in order to reduce selection bias.

In the event of tube dislodgment, the patient will receive same treatment.

Follow-up of patients will occur via chart review until the time of discharge, at 6 months and at 12 months after feeding tube placement via chart review. Data collected will include repeat EGD, length of endoscopy, length of hospital stay, and mortality. The number of endoscopies and repeated nasoenteric tubes placed will be tracked at six and twelve months.

Statistical Analysis

Descriptive statistics (means, medians, percentage) will be used to define the patient characteristics. Chi-square will be used for categorical variables. T-test will be used to analyze continuous variables.

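### The envelope is opened on consent, at no stated procedural step, so the arm may be known before the index tube is placed; opening it just before securing would be a cheap improvement

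*Combined protocol and SAP*

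**What the plan says.** All references are to the combined protocol and SAP.

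- **Who is recruited** (Detailed Description): "Patients to be recruited are those who are scheduled to undergo routine upper endoscopy with nasoenteric tube placement". These are patients scheduled for a tube, not patients who already have one.
- **Consent** (Detailed Description): "Patients will be consented by a member of the research team prior to endoscopy".
- **Opening the envelope** (Detailed Description): clinicians hold randomly generated allocations in sealed opaque envelopes. When a patient has agreed to enter the study, the text continues "trial an envelope is opened and the patient is then offered the allocated treatment regimen". No time or procedural step is given.
- **Blinding** (Detailed Description): "Randomization will be singly blinded only to the patient prior to endoscopy". For the operator: "Endoscopist will not be blinded as they will be placing the securement device and in order to reduce selection bias".
- **Where the arms diverge** (Detailed Description): the control arm has adhesive tape and the device arm a bridle. The bridle takes 1-2 minutes and goes on when the endoscopic procedure is finished. The endoscopy itself is said to be unaffected.
- **Follow-up** (Detailed Description): by chart review until discharge and "at 6 months and at 12 months after feeding tube placement via chart review". Length of endoscopy is among the data collected.
- **Primary objective** (Outcomes): whether the bridle "decreases the need for repeat endoscopy to replace dislodged nasoenteric tubes".
- **Analysis** (Statistical Analysis): descriptive statistics, then "Chi-square will be used for categorical variables. T-test will be used to analyze continuous variables". No analysis set is named, and nothing is said about a patient who is randomised but receives no tube.

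**The concern.** The endoscopist has to know the arm in order to secure the tube. That explains unblinding at securement, not earlier. If the envelope is opened on consent, three things follow.

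1. The index placement is carried out by an operator who may already know the arm. Placement, and the length of endoscopy that is recorded, could then depend on it.
2. Patients enter when placement is scheduled, but follow-up is counted from placement. A patient whose procedure is cancelled or fails after the envelope is opened has been randomised and has no time origin. Excluding such patients may bias the comparison if non-placement, or the decision to exclude, depends on the arm. Counting them as having no event dilutes the risk difference, because a tube that was never placed cannot be dislodged.
3. The reason given for unblinding is unsound. Selection bias is limited by concealing the allocation until the patient is enrolled. An operator who knows the arm does not reduce it.

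**Working it through.** **Order of events.** Set side by side, the statements give: consent (before endoscopy); envelope opened (after consent, step not stated); endoscopy and tube placement; securing by the allocated method; follow-up counted from placement. Opening after placement would still be opening after consent, so the text does not exclude it. Two features favour the earlier reading: the allocated regimen is offered to the patient once the envelope is opened, and the blinding sentence speaks of randomisation in relation to the time before endoscopy.

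**Plan's own figures.** There are none to reproduce. The documents give no sample size, event risk, power or non-placement rate. Everything below is an illustration under assumptions.

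**Assumptions.** Primary outcome taken as a proportion; two-sided alpha 0.05; 1:1 allocation; pooled two-proportion formula; risks p1 = 40% (tape) and p2 = 20% (bridle). A share f of consented patients never receives a tube, equally in both arms.

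**Formulas.** With p̄ = (p1 + p2)/2 and n per arm:

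- n = [1.96·√(2p̄(1−p̄)) + 0.8416·√(p1(1−p1) + p2(1−p2))]² / (p1−p2)²
- power = Φ{ [ |p1−p2|·√n − 1.96·√(2p̄(1−p̄)) ] / √(p1(1−p1) + p2(1−p2)) }

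For 40% and 20% with 80% power, n = 81.2, so 82 per arm.

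**Like-for-like comparison: 82 consented per arm in both designs.**

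- *Early opening*, untubed patients counted as no event: n stays 82 and each risk is multiplied by (1−f).
- *Late opening*: untubed patients are not randomised, so the risks stay at 40% and 20% and n = 82(1−f).

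Worked case, f = 10%:

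- Early: risks 36% and 18%, p̄ = 27%. Power = Φ[(0.18·√82 − 1.2306)/0.6148] = Φ[(1.6300 − 1.2306)/0.6148] = Φ(0.650) = 74.2%.
- Late: n = 73.8. Power = Φ[(0.20·√73.8 − 1.2702)/0.6325] = Φ[(1.7181 − 1.2702)/0.6325] = Φ(0.708) = 76.1%.

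| f | Risk difference, early (points) | Risk ratio, early | Power, early | Power, late | Gap (points) |
|---|---|---|---|---|---|
| 5% | 19 | 0.5 | 77.4% | 78.3% | about 1 |
| 10% | 18 | 0.5 | 74.2% | 76.1% | about 2 |
| 20% | 16 | 0.5 | 67.2% | 71.0% | about 4 |

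The risk ratio stays at 0.5 because (1−f) cancels, for example 18%/36%.

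**Number to consent per arm for 80% power.** Early opening needs 88, 95 and 111 at f = 5%, 10% and 20%. Late opening needs 82/(1−f), that is 87, 92 and 103. At f = 1% and 2% the two designs need the same number: 83 and 83, then 84 and 84.

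**Other assumed risks, f = 10%.** For 30% and 15% the base is 121 per arm, with 138 to consent (early) against 135 (late). For 50% and 25% the base is 58, with 69 against 65.

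No size of bias is computed. That would need non-placement or exclusion rates by arm, and the documents give none.

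**The case against.** The strongest reply is that this is a request for clarification. Early knowledge of the arm is an inference, and sealed opaque envelopes opened only after consent give reasonable concealment at enrolment. The endoscopy is said to be unaffected, and no mechanism is shown by which knowing tape or bridle would alter the index placement. Defining the analysis set would settle the untubed patients without moving the envelope. The change also leaves the larger exposure, the unblinded decision to repeat endoscopy, where it was.

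Most of this stands as a limit on the point. Three stronger readings are tempting, and the documents do not support them:

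- *That allocation concealment fails, or that index placement is biased.* The text describes concealment until consent. The gap is the interval between opening and securing, and no effect in that interval is shown.
- *That leaving out untubed patients forfeits the randomised comparison.* It does so only if non-placement or exclusion depends on the arm. If it does not, restricting to patients with a tube leaves the comparison unbiased.
- *That early opening costs about 3, 6 or 13 points of power.* Those figures set 77%, 74% and 67% against 80% in a trial that loses nobody. Late opening also loses the untubed patients, who are simply not randomised, so the fair comparison holds the number consented fixed.

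What does not stand is that the matter is only missing detail. The stated sequence permits a dependence that the design has no use for, and one change of timing removes it. An analysis-set rule alone would not keep the index placement independent of the arm.

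**Conclusion.** The point holds as a worthwhile, inexpensive design improvement. As written, the plan allows the arm to be known before the index tube is placed, and it randomises patients who may never have a start to their follow-up. Neither is needed for a comparison of securing methods.

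The size is modest. The gap of about 1 to 4 points of power rests on the assumed 40% and 20% risks, on 5% to 20% non-placement equal in both arms, and on counting untubed patients as event-free. The non-placement range has no source in the documents, and with little non-placement the gap all but disappears. The direction and size of any bias cannot be established. The sentence on selection bias should be corrected whatever is decided about timing.

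**What to change.** **Preferred.**

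- Obtain consent to either arm before endoscopy.
- Open the next sequentially numbered envelope only when the tube is placed and the scope withdrawn, immediately before securing. Record the endoscopy end time before opening it.
- Analyse all patients whose envelope was opened, by allocated arm, with follow-up from that point. Report consented patients who were not randomised.
- Rewrite the sentence under which the allocated regimen is offered after opening, so that it matches the new order.
- Delete the claim that an unblinded endoscopist reduces selection bias, and state that the arm is unknown to the endoscopist until the index tube is placed.

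**If opening on consent is kept.** Say so explicitly, analyse all randomised patients by allocated arm with follow-up from randomisation, and state how patients without a tube are counted.

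**Cost.** A few protocol sentences and no extra procedure. An envelope and a bridle kit must be at hand for every case, patients must accept either arm in advance, and some consented patients will not be randomised. In the scenarios above this does not raise the number to be consented.

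**Limit to state in the protocol.** The change protects the index placement only. The arm remains known at repeat procedures and when the decision to repeat endoscopy is made.

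### Would a t-test on length of hospital stay mislead because it counts an in-hospital death like a live discharge?

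*Combined protocol and SAP*

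**What the plan says.** Length of stay appears once in the combined protocol and SAP, in the follow-up paragraph of the Detailed Description: "Data collected will include repeat EGD, length of endoscopy, length of hospital stay, and mortality". It is not defined there, and nothing says how a patient who dies in hospital is scored.

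The Statistical Analysis section has two inferential rules: "Chi-square will be used for categorical variables" and "T-test will be used to analyze continuous variables". The first covers mortality. The second is the only one that could cover stay.

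Under Outcomes, the primary objective is the need for repeat endoscopy to replace dislodged tubes, and the secondary is dislodgement: "Secondary objectives can assess if reduces tube dislodgement frequency". Stay is in neither. The same section gives the hypothesis that bridles will "reduce the number of unnecessary endoscopies reducing health care costs and complications".

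**The concern.** A t-test uses only the number of days. If all patients enter with their observed stay, a death on day d and a live discharge on day d are the same observation. The Brief Summary sets the trial in critically ill patients, so in-hospital deaths are plausible. If one arm truly had more deaths, and they came earlier than discharge would have, that arm would show a shorter mean stay. A reader who took shorter stay as faster recovery would then draw the wrong conclusion. Mortality is collected, but the plan does not link the two.

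**Working it through.** The documents give no sample size, mortality, length of stay or significance level, so there is no figure of the plan's to reproduce. Every input below is an assumption: mean stay 20 days for live discharges, in-hospital mortality of 20% in one arm and 20% to 30% in the other, 75 per arm, two-sided 5%.

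**Bias in mean stay.** Let p be in-hospital mortality, S the mean stay of those discharged alive and D the mean day of death. Mean stay is (1 − p)S + pD. If S and D are the same in both arms, the difference between arms is

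(difference in p) × (D − S).

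- 10-point difference, D = 8: 0.10 × (8 − 20) = −1.2 days
- 10-point difference, D = 28: 0.10 × (28 − 20) = +0.8 days
- 2-point difference: 0.02 × (8 − 20) = −0.24 days to 0.02 × (28 − 20) = +0.16 days
- Equal mortality and timing: 0

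The direction depends on when deaths occur. It vanishes at D = S and reverses for late deaths.

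**Constant hazards.** With a live-discharge hazard of 1/20 per day in both arms, mean stay is 20(1 − p): 16.0 days at 20%, 15.6 at 22% and 14.0 at 30%. Stay is exponential, so its SD equals its mean. At 20% vs 30% the standard error of the difference is √[(16² + 14²)/75] = 2.46 days, and 2.0/2.46 = 0.81. The normal approximation puts the chance of a significantly shorter stay in the higher-mortality arm at about 12.6%; simulation gives 12.4%.

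**Simulated chance that the higher-mortality arm has a significantly shorter stay** (2.5% expected with no bias; 10,000 trials per setting, 6,000 for mixed severity):

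| Model | 20% vs 20% | 20% vs 22% | 20% vs 25% | 20% vs 30% |
|---|---|---|---|---|
| Constant hazards | 2.4% | 3.2% | 5.8% | 12.4% |
| Gamma stays, deaths averaging day 8 | 2.3% | 3.0% | not run | 7.8% |
| Gamma stays, deaths averaging day 14 | not run | not run | not run | 4.6% |
| Gamma stays, deaths averaging day 20 | 2.4% | 2.5% | not run | 2.5% |
| Gamma stays, deaths averaging day 28 | 2.4% | 1.8% | not run | 1.2% |
| Mixed severity | 2.0% | 3.8% | 8.7% | 26.7% |

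In the mixed-severity model, half the patients are discharged more slowly (1/30 against 1/10 per day) and bear all the deaths. Overall mortality of 20% vs 30% therefore means 40% vs 60% in that half.

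**Would the usual alternative do better?** The natural replacement is a log-rank test of live discharge with deaths censored.

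- Under constant hazards at 20% vs 30%, it finds the higher-mortality arm faster in 2.6% of trials. That is guaranteed by construction, since both arms share one discharge hazard.
- Under mixed severity it gives 5.7%, well below the t-test.
- In the gamma setting, where patients who will die are never candidates for discharge, it finds the higher-mortality arm significantly slower in 4.4%, 6.8%, 10.1% and 14.9% of trials (deaths averaging day 8, 14, 20 and 28). The t-test's larger one-sided rates are 7.8%, 4.6%, 2.5% and 4.6%; at day 28 this is the longer-stay side.

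The log-rank test therefore reacts to deaths more than the t-test at three of the four timings. Those are not false positives for its own question, but that question is the rate of live discharge, not days in hospital.

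**The case for a change.** The best case for a change is that the plan collects stay, has one blanket rule for continuous data and is silent on deaths, so an analyst following it literally would mix deaths with discharges. The cost hypothesis makes a comparison of stay likely to be reported. Leaving deaths out instead would condition on an event after randomization. A few sentences, plus discharge status and dates, would let readers separate recovery from death.

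The silence is real, and the arithmetic is right for the inputs assumed. Three things limit what follows:

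- Equal counting is inferred from silence. The plan does not say stay will be compared, and a survivors-only t-test would fit its wording as well.
- Equal counting is wrong only if stay is read as recovery, a reading the documents never give it. For resource use, a patient who dies on day d did occupy a bed for d days. A sensible remedy would keep the difference in mean bed-days with a 95% confidence interval, which carries essentially the same information as the t-test.
- The larger rates need a true mortality gap of 5 to 10 points. The arms differ only in tape versus bridle, and the Detailed Description says of bridle placement "No addition sedation, medication or exposure necessary". The only link to death is through endoscopic placement itself, where the Brief Summary says "there is risk of perforation, infection, bleeding, aspiration, and rarely even death".

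**Conclusion.** No change to the plan is needed. This is missing detail on a variable that is not an objective, and analysts can fill it sensibly by treating total stay as bed-days and showing in-hospital mortality by arm beside it. The t-test keeps its error rate when the frequency and timing of death are equal; chance imbalance in deaths is already within the 5%. At a 2-point mortality difference, the chance of a significantly shorter stay in the higher-mortality arm stays between 1.8% and 3.8% across the models run. Distortion becomes material only if stay is read as speed of recovery and true mortality differs by several points, and a gap of that size could be looked for in the mortality comparison. Replacing the t-test with a live-discharge analysis would be a choice of a different estimand, not a clear gain. The primary and secondary objectives are untouched. The sizes rest wholly on assumed mortality, timing, stay and sample size.
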